## Materials

Researchers created a 25-minute loneliness SSI and a 3-week loneliness intervention by adapting Käll et al.'s 9-week therapist-supported iCBT for loneliness (Käll, Shafran, et al., 2020). Käll et al.'s iCBT focuses on person-level psychological factors contributing to the maintenance of loneliness; it aims to help challenge maladaptive thoughts and encourage social behaviors (more information on Käll et al.'s iCBT available at [www.iterapi.se/sites/solus/](http://www.iterapi.se/sites/solus/)) (Käll, Shafran, et al., 2020). Following Käll et al.'s iCBT, the loneliness intervention includes content relating to understanding loneliness, setting goals and values, testing thoughts and behaviors, making plans, gaining social confidence, and overcoming barriers. Broadly, the intervention uses behavioral activation, cognitive restructuring, and behavioral experimentation strategies. The loneliness interventions also pull content from Jessica Schleider et al.'s single-session mental health interventions (<http://www.schleiderlab.org>) and take inspiration from their interventions' aesthetics and their strategy of using Qualtrics to develop and provide the intervention. Both the 30-minute SSI and 3-week intervention are text-based and self-guided.

The 3-week intervention includes three 10-20-minute self-guided sessions (participants complete the first session when they start the study, the next session a week later after they receive an email with it, and the final portion the next week when they receive another email).

In the control condition, participants complete a supportive therapy SSI, called "The Sharing Feelings Project", of roughly equivalent length and style to the loneliness SSI (J. L. Schleider & Weisz, 2019). The supportive therapy SSI, which researchers

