## **Hypotheses**

Researchers’ primary hypothesis is that participants randomized to the loneliness SSI will have greater reductions in self-reported loneliness between baseline and 8-week follow-up than those who are randomized to the active control SSI.

As secondary hypotheses, researchers predict greater improvements in distress (DASS-9), social anxiety, general self-efficacy, hopelessness, meaning and purpose in life, and adaptive actions and thoughts in the loneliness SSI condition relative to the control SSI. Researchers also hypothesize that participants who are randomized to the 3-week version of the loneliness intervention will report greater reductions in loneliness than those who are randomized to either the control condition or the 30-minute SSI.

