### *Exploratory Hypotheses*

1. Having an insight experience during the intervention is associated with greater improvement in mental health outcomes between baseline and week 8.
2. Greater self-efficacy at baseline is associated with greater reduction in loneliness between baseline and week 8.
3. Greater engagement with the SSI platform predicts greater improvement in loneliness between baseline and week 8.

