2. To test if baseline self-efficacy is associated with change in loneliness between baseline and week 8, researchers will run a mixed-effects model with loneliness as the outcome, timepoint, baseline self-efficacy (as measured by the GSE-6), and the interaction between the two as predictors, and a participant identifier nested within experimental condition as a random intercept.
3. To test if engagement with the intervention predicts change in loneliness, researchers will run a mixed-effects model with loneliness as the outcome, timepoint, engagement (measured as the number of characters entered across all text entry prompts within interventions), and the interaction between the two as predictors, and participant identifier nested within experimental condition as a random intercept.

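### Study 1's engagement model pools raw character totals over one three-session and two one-session programs with no time-by-condition term, so arm differences can pass as an engagement effect

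*Combined protocol and SAP*

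**What the plan says.** Under Aim 1, Exploratory Hypotheses, the third hypothesis reads "Greater engagement with the SSI platform predicts greater improvement in loneliness between baseline and week 8". The matching model is item 3 of the additional analyses testing exploratory hypotheses. Its outcome is loneliness and its fixed effects are timepoint, engagement and their interaction. Engagement is "engagement (measured as the number of characters entered across all text entry prompts within interventions". Condition appears only in the random part: "participant identifier nested within experimental condition as a random intercept".

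The item mentions no transformation, cap, scaling by prompt or session, restriction to an arm, or time-by-condition term. By contrast, the engagement models of Study 2 are expressly restricted to two of its three conditions.

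The programs differ in structure. Under Materials, "The 3-week intervention includes three 10-20-minute self-guided sessions", with sessions 2 and 3 sent by email in later weeks. The loneliness SSI is one session, described once as 25 minutes ("Researchers created a 25-minute loneliness SSI and a 3-week loneliness intervention") and once as 30 minutes ("Both the 30-minute SSI and 3-week intervention are text-based and self-guided"). The control is "of roughly equivalent length and style to the loneliness SSI".

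Under Hypotheses, the plan expects the arms to change by different amounts: "participants who are randomized to the 3-week version of the loneliness intervention will report greater reductions in loneliness" than those in either other condition.

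**The concern.** The quantity of interest is whether people who engage more improve more. A total typed over three sessions and a total typed in one sitting are put on the same scale and pooled. If the three-session program collects more text per person, its participants sit at the high end of the predictor. If that arm also improves more, as the plan predicts, the pooled slope points in the hypothesised direction even when typing is unrelated to improvement inside every arm. The random intercept for condition does not protect against this: it lets arms start at different levels but says nothing about how fast they change.

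At stake is the reading of one exploratory result, tested at p < 0.05. A significant interaction could be reported as a benefit of engagement when it only restates a difference between programs.

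**Working it through.** The plan states no figure for this analysis, so there is nothing to reproduce. The check is what the planned model does when engagement has no effect within any arm.

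**Inputs from the documents.** Total length of the 3-week program is 3 × 10 = 30 to 3 × 20 = 60 minutes; the SSI takes 25 or 30 minutes. The length ratio is therefore 30/30 = 1.0 to 60/25 = 2.4. Alpha is 0.05 (two-sided assumed).

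**Assumptions, because the documents are silent.** Equal arms, 150 each (N = 450); lognormal character counts with log-SD s = 0.5 or 1.0; the 3-week arm typing k times as much as the other two; the 3-week arm improving by d more, in SDs of change; complete baseline and week-8 data. With such data the time-by-engagement coefficient equals the least-squares slope of change on engagement. One fitted mixed model confirmed this (−0.0616 both ways).

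**Formulas.** With mean count m in the two one-session arms and km in the 3-week arm:

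- Between-arm variance of the count: (1/3)(2/3)(k − 1)²m² = (2/9)(k − 1)²m².
- Average within-arm variance: m²(e^(s²) − 1)(2 + k²)/3.
- B = between-arm share of the count's variance.
- C = between-arm share of the variance of change = (2/9)d² / (1 + (2/9)d²).
- Correlation created by arm alone: r = √(B × C).
- z = r√N / √(1 − r²); rejection rate = Φ(z − 1.96) + Φ(−z − 1.96).

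**Worked case, k = 2, s = 0.5, d = 0.3.** e^0.25 − 1 = 0.284. Between: 2/9 = 0.222. Within: 0.284 × 6/3 = 0.568. B = 0.222/0.790 = 0.281. C = 0.02/1.02 = 0.0196. r = √(0.281 × 0.0196) = 0.074. z = 0.074 × 21.2/0.997 = 1.58. Rejection is about 35%; simulation (1,000 runs) gave 37%.

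**Range at 150 per arm, no engagement effect within any arm.**

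| log-SD s | typing ratio k | arm difference d | B | formula | simulated |
|---|---|---|---|---|---|
| 0.5 | 1.5 | 0.2 | 12% | 11% | 11% |
| 0.5 | 2 | 0.3 | 28% | 35% | 37% |
| 0.5 | 3 | 0.5 | 46% | 92% | 93% |
| 1.0 | 1.5 | 0.2 | 2% | 6% | 5% |
| 1.0 | 2 | 0.3 | 6% | 11% | 13% |
| 1.0 | 3 | 0.5 | 12% | 40% | 45% |

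With equal typing (k = 1) the simulated rate is 4.1% to 5.6% at any d. With equal change (d = 0) and k of 1.5 to 3 it is 4.1% to 6.1%. Both differences are needed. The middle case at s = 0.5 gives 16% at 50 per arm and 63% at 300, so the distortion grows with sample size.

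**Does the planned intercept help?** In one fitted example an added arm intercept (fixed, standing in for the planned random one) left the slope at −0.0616, p = 0.028. Adding time-by-arm moved it to 0.013, p = 0.72.

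**Do the remedies work?** Over the six table settings (2,000 runs each), standardising characters within condition gave 3.8% to 5.4% rejection, and adding time-by-arm to the raw count gave 3.7% to 5.9%. Taking logs alone does not help: 38% in the middle case at s = 0.5.

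**The case against.** The strongest reply is that the documents do not show that the arms type differently. They give no prompt counts, return rates or distribution of characters. More sessions need not mean more prompts, and the stated lengths allow a ratio of 1.0, where there is no distortion. A typing ratio of 3 exceeds the largest length ratio, 2.4, so the top of the range needs more text per minute in the 3-week arm. All of this stands, and it is why the point is conditional. It does not remove the problem: k = 2 lies inside the length range, and with d = 0.5 and s = 0.5 it gives 74%.

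A reader might infer something stronger: that a few long writers, or the arm with the most prompts, determine the slope. That is not established. In simulation the top 5% of writers hold 32% of the raw count's sum of squares at log-SD 0.25 and 80% at 1.25, and nothing in the documents says which applies. High leverage is also not bias; a linear model gives more weight to widely spread values by design. The two mechanisms partly offset each other, since stronger skew shrinks the between-arm share (28% at s = 0.5, 6% at s = 1.0, with k = 2).

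Nor do the documents support replacing the measure with log characters. The efficiency argument is symmetric: if improvement is linear in characters, taking logs loses as much as raw counts lose in the opposite case. Zero counts are also foreseeable, because the covariate-adjusted analysis of Study 1 includes an indicator for having answered at least one written question. Under an assumed median of 500 characters among writers, n = 300 and log-SD 0.8 to 1.2, 5% zeros would hold about 55% to 71% of the sum of squares of log(1 + characters). Scoring the 3-week arm on session 1 alone does not give a like-for-like comparison either: that session lasts 10 to 20 minutes against 25 to 30 for the SSI. Returning and writing more is arguably engagement too.

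**Conclusion.** The point holds as a gap in the specification. Item 3 as written does not separate engagement from arm. If the arms differ both in characters typed and in loneliness change, its time-by-engagement slope mixes the two. At 150 per arm, over the assumed ranges, the false-positive rate runs from about 5% (no inflation) to about 90%, with 37% in the middle case at log-SD 0.5 and 13% at log-SD 1.0. These figures rest on assumed counts, sample size and arm difference; only the expected direction of the arm difference comes from the plan.

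There is also a mismatch of scope: the hypothesis speaks of the SSI platform, while the model as written includes a program that is not single-session. Importance is low. This is one exploratory association and has no bearing on the primary analysis.

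**What to change.** In item 3, keep the character total but standardise it within condition, or add condition and time-by-condition as fixed effects. Report the time-by-engagement slope for each arm, and show the loneliness SSI slope separately because hypothesis 3 refers to the SSI. State whether the 3-week arm is part of the test of that hypothesis.

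A log-character model and a session-1-only score for the 3-week arm may be added as sensitivity checks, with people who typed nothing handled separately, for example by their own indicator. They should not replace the stated measure.

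The cost is one recoding line or two model terms, plus a sentence or two in the analysis plan. With standardisation the coefficient is no longer per character, and per-arm slopes are less precise than a pooled one. Fixing the choice before looking at this association keeps the handling of arm from becoming a post hoc decision.

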### Tables describing measures

**Table 1.** Full list of primary, secondary, and screening variables collected during the study, including when during the trial they were assessed.

Measure (Primary, Secondary, Other)	Baseline	Post- Intervention	4-week follow-up	8-week follow-up
UCLA Loneliness Scale (primary)	X		X	X
Depression Anxiety and Stress Scale – Short Form (secondary)	X		X	X
3-item Mini Social Phobia Inventory (secondary)	X		X	X
Short form of the General Self-Efficacy Scale (secondary)	X	X	X	X
Beck Hopelessness Scale – 4-item (secondary)	X	X	X	X
Frequency of actions and thoughts scale (secondary)	X		X	X
Program Feedback Scale (secondary)		X		
Credibility and Expectancy Questionnaire (secondary)		X		
Insight experience (secondary)		X		
Star rating (secondary)		X		
MacArthur Scale of Subjective Social Status – Youth Version (secondary)	X			
UCLA loneliness scale – 3 item (screening)	X			
Patient Health Questionnaire – 4-item (screening)	X			

**Table 2.** Measures organized by dimension

Dimension	Application to project	Study Measurement(s)
Effectiveness	Improvements in symptoms and functioning	Primary: ULS-20 (loneliness) Secondary: DASS-9 (depression, anxiety, and stress), Mini-SPIN (social anxiety), GSE-6 (general self-efficacy), Beck Hopelessness Scale, FATS (frequency of adaptive behaviors and thoughts related to therapeutic change),
Engagement	Satisfaction with intervention and aspects of experience	Intervention appeal: PFS (satisfaction with SSI), CEQ (intervention credibility and expectations of impact), insight experience, frequency of using one's list of popular online content links, insight experience, star rating (program quality)
Screening	Inclusion in main analyses and reimbursement	ULS-3 (loneliness), PHQ-4 (depression/anxiety)

## **Study 2: Trial of a popular online content-based single-session intervention for psychological distress**

### **Procedure**

#### *Sample recruitment*

Researchers will use social media and the University of California, Irvine Social Ecology subject pool to recruit a diverse online sample of English-speaking participants aged 16+ with access to the internet and a computer, tablet, or smartphone. To advertise the study on social media, researchers will use both paid and unpaid posts on several social media platforms, potentially including Instagram, Reddit, Tumblr, Twitter, Facebook, LinkedIn, 4chan, and others.

Researchers may also use the online subject recruitment platform Researchmatch. Finally, researchers may collaborate with Healthy Gamer, a web-based mental wellness company, to share information about the study with Healthy Gamer's online community Discord and Subreddit, reaching 20,000-25,000 people.

To ensure a sufficient number of participants for analysis who are experiencing distress, if one's score on the PHQ-4 meets the study criterion for "struggling with distress", one will be offered reimbursement of a \$10 Amazon gift card that researchers will email them once they complete the final follow-up 8 weeks later, provided they completed all 4 evaluations (pre-test, post-test, 4-week, and 8-week). Participants will be considered to be struggling with distress if their score on either the depression or anxiety subscale is at least 3 (range 0-6), as these scores are suggestive of a depressive or anxiety disorder (Kroenke et al., 2009).

Participants who do not meet the criterion for "struggling with distress" will still have the opportunity to complete the study without compensation. They will also be allowed to access the *ABC Project* and *Blu Surfer* programs directly if they prefer to not participate in the study. Participants are only allowed to complete the study once.

Those who participate through the UC Irvine subject pool will receive 1 hour of participation credit for completing the first part of the study. If UC Irvine subject pool participants meet criteria for struggling with distress, they will also be offered a \$10 gift card for completing all parts of the study.

#### *Study process*

Participants will first complete the PHQ-4 measure, which will determine if they are offered a \$10 gift card for their participation in the study in the study information portion. After participants read the study information and agree to participate, they complete baseline self-report measures of mental health outcomes and demographics. Next, they complete the intervention (see Materials section below for intervention information). After completing the intervention, participants are offered access to a browser and PDF version of the intervention they completed to keep and/or share with others. They are also referred to other online resources for people struggling with mental health. Next, they complete a few brief measures of hope, agency, meaning in life, and engagement with the intervention platform. 4 and 8 weeks later, they receive links via email to complete follow-up measures of mental health outcomes and engagement. At the end of the 8-week follow-up, participants are given access to all three conditions in PDF and browser forms. The entire study is conducted using the secure online experience management platform Qualtrics and several anti-fraud / bot measures are included in the survey. All contact between researchers and participants is asynchronous.

## Materials

The experimental condition will be the *Blu Surfer* Program, a 25-minute SSI that the research team developed centered on popular online content relevant to mental health. In the SSI, each user is first asked to select the kinds of support they would like to view. Next, the user is asked to explore a library of annotated popular online content (filtered by the kinds of support they chose) and to select the content they find personally valuable. Researchers crowdsourced this library by asking people from a range of online communities and an undergraduate psychology course lecture to contribute one piece of popular online content that they believed could help someone overcome a difficult time or mental health challenge in their life. Finally, the SSI provides the user a list of the content they selected to keep and draw from, build on, or share with friends.

The active comparison condition will be the *ABC (Action Brings Change) Project* (TEAM Lab Version). The original *ABC Project* is a 30-minute SSI for teens based on behavioral activation that was found to be efficacious for reducing depression, anxiety, hopelessness, and self-hate and increasing perceived control and agency in youth (link to SSI: <https://osf.io/ch2tg/>, license: <http://creativecommons.org/licenses/by-nc-sa/4.0/>). The TEAM Lab version slightly modifies the intervention to make it more relevant to both teens and adults.

The third condition is *online help-seeking as usual*, which aims to emulate how one might find support using the internet on one's own. In this condition, participants are asked to browse the internet for 25 minutes to find popular online content for overcoming personal problems and create an annotated list of links to the content they find personally useful. This condition is similar to the “self-study” condition in another study that found self-study and a video intervention equally increased mental health knowledge (Yamaguchi et al., 2019). The survey platform provides text entry boxes to help each participants create their guide and then provides a text version of their guide for them to keep.

## Hypotheses

Researchers' primary hypothesis is that participants randomized to the *popular online content SSI (The Blu Surfer Program)* will have greater reductions in distress between baseline and 8-week follow-up than those randomized to the *researcher-created SSI (the ABC Project)*.

As secondary hypotheses, researchers predict greater improvements in loneliness, general self-efficacy, hopelessness, meaning and purpose in life, and adaptive actions and thoughts in the *popular online content SSI* condition relative to the *researcher-created SSI*. Researchers also predict that participants randomized to the *popular online content SSI* will report greater reductions in distress than those randomized to the *online help-seeking as usual* condition.

### *Exploratory hypotheses:*

1. Demographics and baseline mental health characteristics predict one's willingness to choose a certain kind of content.
2. The kinds of content one chooses predict change in distress between baseline and 8-week follow-up.
3. Participants add more pieces of content to their guide when provided an annotated library to choose from VS when they have to seek out their own content without a library.
4. Participants are more satisfied with their mental health resource guides after completing it when they choose content from an annotated library than when they choose it themselves.
5. Participants are more likely to view their mental health resource guide after 8 weeks when they choose content from a curated library than when they select it all on their own.
6. Younger participants will experience a greater reduction in distress after the popular

online content interventions than older participants at 8 weeks.

7. The annotated library condition (*blu surfer*) is more likely to lead to an insight experience than online help-seeking as usual.
8. Having an insight experience during an intervention is associated with greater improvement in distress at 8 weeks.
9. Higher baseline general self-efficacy is associated with greater improvement in distress at 8 weeks.
10. Engagement with the SSI predicts greater improvement in distress at 8 weeks.

## **Analysis Plan**

The main DV is the change between baseline and 8-week follow-up in distress, measured by the total score of the Depression and Stress Scale - 9 item version.

### *Main analysis*

The main analysis compares change in distress from baseline to 8-week follow-up across experimental conditions. Researchers will use a mixed-effects model predicting distress with condition, measurement time point (1 = baseline, 2 = 4-week follow-up, 3= 8-week follow-up), and the 2-way interaction between condition and measurement time point as IVs and a participant identifier as a random intercept. Using the “lme4” package in R, this analysis will take the following form:

```
lmer(distress ~ time*condition + (1|study_id))
```

### *Secondary analysis*

Researchers will re-run the main analysis separately for each secondary outcome, although the timepoints measured by the “time” variable will differ across outcomes (see table 3).

### *Inclusion criteria*

Main analyses will be limited to only those participants who 1) met criteria for struggling with distress, 2) were randomized to a condition (ie, those who consented to participate and completed the baseline measures), 3) did not indicate that they did not participate seriously at the end of the study, 4) completed the study only once, and 5) were not clearly bots, responding mischievously,

or speeding past most of the content. Researchers will examine whether a response is fraudulent on a case-by-case basis, taking the suspicious factors mentioned in study 1's inclusion criteria into account.

